**25. Appendix 12: English - Modified Alcohol Use Disorders Identification Test-Consumption**

Modified Alcohol Use Disorders Identification Test-Consumption (AUDIT-C)					
PART ONE: pre-admission alcohol use					
Questions	0 points	1 point	2 points	3 points	4 points
In the 3 months before you were admitted to the hospital, on average, how often did you have a drink containing alcohol?#	Never	Monthly or less	2-4 times a month	2-3 times a week	4+ times a week
When you were drinking alcohol, on average, how many drinks did you have?*	0-2	3-4	5-6	7-9	10 or more
When you were drinking alcohol, on average, how often did you have 6 or more drinks* in one day?	0	Less than monthly	Monthly	Weekly	Daily or almost daily
PART TWO: post-discharge alcohol use					
Questions	0 points	1 point	2 points	3 points	4 points
Since discharge, on average, how often have you had a drink containing alcohol?	Never	Monthly or less	2-4 times a month	2-3 times a week	4+ times a week

When to refer for counseling for unhealthy alcohol use:
 
 
Score of 3 or more pre-admission and 2 or more post-discharge
 
Score of 3 or more post-discharge, regardless of pre-admission score
 
					

Footnotes:

#If the person reports never drinking (i.e., abstinence), leave next two blank (skip them)

\*Standard drink units can be determined as follows:

- 1 **lager** (12-ounce bottle, Mosi/Castle, 3% alcohol) = 1 unit
- 1 glass of **wine** (5-ounce, 10% alcohol) = 1 unit
- 1 container of **opaque beer** (1-liter, Chibuku Shake Shake, etc., 4% alcohol) = 4 units
- 1 bottle of **spirits** including gin, vodka, 'junta', 'twojilijili' (200 ml bottle; 40% alcohol) = 8 units
- 1 bottle of **Cachasú** (200 ml bottle; >40% alcohol) = 10 units

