## **2. Background Information and Scientific Rationale**

### **2.1 Background Information**

Hospitalization presents a potential opportunity to alter the long-term outcomes of persons living with HIV (PLHIV) in sub-Saharan Africa (SSA). HIV-related hospital admissions remain common despite mature antiretroviral therapy (ART) programs, and while inpatient mortality rates are 10-30%, an additional 20-40% die within 1 year of discharge. Most hospitalized PLHIV are ART-experienced and had history of poor retention in care and viral suppression. For example, at a central hospital in Zambia, ~90% of hospitalized PLHIV had prior/current ART use (median of 30 months) and 50% of ART-experienced individuals were not virally suppressed, many of whom had disengaged from care. Current inpatient care focuses on stabilization and neglects to understand and intervene on the underlying reasons for suboptimal care engagement that contributed to the hospitalization. Discharge transition of care models for hospitalized PLHIV are virtually non-existent.

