### **4.3 Exploratory objectives**

1. To explore barriers and facilitators to the HIV care cascade for PLHIV following hospitalization
2. Describe the prevalence of behavioral health comorbidities after hospital discharge among people with HIV
3. To investigate the impact of HIV-associated coinfections and comorbidities on post-hospital outcomes.
4. To explore experiences of community health workers with the delivery of a post-discharge community based CHW follow-up model for adults with HIV
5. To characterize the prevalence of mental health co-morbidities such as depression among PLHIV during and following hospitalization

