- **Outpatient follow-up verification:** At the first visit (within one week), the CHW will discuss with patient and care giver the timing and location of follow-up. They will remind the client by phone 1 day before and if the patient misses that visit, the CHW will arrange to

accompany the patient to the clinic at the soonest possible time. In Zambia, the standard post-hospital follow-up at outpatient occurs at 2 weeks.

- **Identify knowledge gaps among patient and family related to the reason for illness:** The CHW will document the reason for illness and the family's and patient's understanding of the illness and list any questions they have.
- **Screening for behavioral health comorbidities:** The CHW will screen for symptoms of depression and unhealthy alcohol use at ~1 month after discharge and make referrals as feasible.
- Conduct a quick home observation to document the patient home environment to assess barriers existing as well as facilitators to engagement.

To ensure that CHWs are fully supported, they will meet with CLO once per week to discuss their clients. CLOs reinforce adherence to the model. The CHW will also call their CLO supervisor urgently from the client household if certain parameters are outside of range, such as elevated pulse. The CLO can then engage the physician as needed.

The ReCharge CHW intervention holds promise. First, it was designed based on a rigorous local formative project (ReCharge 1) and with inputs from clinical, community, and program experts and MOH. Also, CHW support is both highly feasible and acceptable, but can reduce death in PLWH. In the REMSTART trial, weekly home visits plus testing and treatment of cryptococcal disease among people with low CD4 reduced mortality significantly. Many of our clients will have CD4 >200; however, given their recent hospitalization, they are at high risk of mortality.

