#### **5.2.4 Quantitative outcomes:**

Our primary effectiveness outcome will be alive and virally suppressed at 6 months after hospital discharge. Patients who either pass away or have a viral load >60 copies/ml will be considered failures. Patients who are alive but have unknown VL will also be considered failures. Those who transfer care outside of Lusaka District (we expect this to be 2-3%, based on a prior study) will be censored. We will also evaluate numerous secondary outcomes, including retention on ART, defined as possession of ARVs within 30 days of the 6-month post-discharge time point, consistent with PEPFAR TX\_CURR definition. We will also assess ARV adherence (based on medication possession ratio), number of visits attended, and the rate of hospital re-admission.

To ascertain these outcomes, our research assistant will contact the client each month post-discharge to check vital status (alive versus dead) and whereabouts. At 6 months after discharge, we will confirm the location of last HIV care and arrange for patient to have HIV VL, either back at the hospital or at their local clinic. The team will extract electronic medical records from the clinic including visit, pharmacy, and laboratory data, including HIV viral load results. Transfers within Lusaka (where there are 30+ ART clinics) are common and this approach will allow us to have complete end-line data for most clients, including historical controls and pilot participants.

We will also collect implementation outcome data during the trial, such as proportion of trial participants who do not receive any CHW services, the number and type (phone calls, home visits, meetings at the facility) of interactions between participants and CHWs. Semi-structured interviews with a subset of patients will be done to check acceptability of the intervention.

To begin to understand and anticipate meaningful patterns in our pilot data, we will also collect socio-demographics and socio-economic data on patients and their households, as well as capturing extent and severity of co-morbidities. We will include the following measures, captured at the following time points:

At enrollment/in hospital:

- Education (highest completed grade attained) for patient and primary caregiver
- Age, marital status, number of children
- Relationship to household head
- Religion and religiosity (affiliation, frequency of church attendance (weekly))

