- Distance to referral health clinic and to referring hospital (time takes to get to clinic / mode of transit)

At one month:

- Mental health screening (PHQ)
- Alcohol screening (AUDIT)
- Household food insecurity (HFIES scale)
- Household asset-based wealth index (DHS module)

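### The pre-admission alcohol questions are asked only at about 1 month after discharge, so patients who die or are not reached before then have outcomes but no pre-admission alcohol score

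*Combined protocol and SAP*

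**What the plan says.** Appendix 12 splits the alcohol screen in two. Part One has three items on the period before admission, opening with "In the 3 months before you were admitted to the hospital, on average, how often did you have a drink containing alcohol". Part Two has one item: "Since discharge, on average, how often have you had a drink containing alcohol". The referral rule beneath them uses both scores.

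The screen is scheduled once. Section 5.1 states: "The CHW will screen for symptoms of depression and unhealthy alcohol use at ~1 month after discharge". Section 5.2.4 lists alcohol screening among the one-month measures. Its list headed "At enrollment/in hospital" covers education, age, family, religion and distance to care, with no alcohol item. The only earlier mention of drinking is an open probe in the first qualitative interview (Appendix 1), which is planned for 24 patients and yields no score.

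The mortality, readmission and retention endpoints in Section 4.5 start at discharge. Section 5.2.4 counts a death as a failure of the alive-and-suppressed outcome. The protocol does not say how patients without a 1-month screen are handled.

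**The concern.** Drinking before admission is fixed history by the time a patient is enrolled. Collecting it a month after discharge makes its availability depend on surviving and being reached for that month, which is part of the outcome period.

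Two uses could be affected. Section 4.3 includes the objective "To investigate the impact of HIV-associated coinfections and comorbidities on post-hospital outcomes", and Section 5.2.4 says that these measures are collected to help understand patterns in the pilot data. Section 8.2.1 adjusts the comparison with controls for potential confounders, which it does not name. If the pre-admission score enters either analysis on complete cases, every first-month death drops out, and all of these are failures. The adjusted and crude results would then describe different sets of patients.

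Section 5.1 makes the screen a CHW task, and the protocol does not say whether the historical controls are screened for alcohol at all.

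**Working it through.** The protocol gives no first-month death rate and no expected completeness for the 1-month screen, so there is no stated figure to reproduce.

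**Inputs**
- One-year mortality M: Section 2.1 says "an additional 20-40% die within 1 year of discharge". I take this as a share of those discharged, so M = 0.20 or 0.40.
- Shape of the death curve: not given. I assume a Weibull curve with shape k = 1 (constant hazard) or k = 0.5 (front-loaded).
- Survivors not reached at 1 month: not given. I assume 0% or 10%.

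**Deaths before the screen**

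With t in years, the proportion dead by t is F(t) = 1 − (1 − M)^(t^k). For M = 0.20 and k = 1, F(1/12) = 1 − 0.80^(1/12) = 1.84%, F(1/2) = 1 − 0.80^(1/2) = 10.56%, and the share is 1.84/10.56 = 17.5%. Patients scored per 100 are 100 × (1 − F(1/12)) × (1 − proportion not reached).

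| M | k | Dead by month 1 | Dead by month 6 | Share of 6-month deaths unscored | Scored per 100 (0% / 10% not reached) |
|---|---|---|---|---|---|
| 20% | 1 | 1.84% | 10.56% | 17.5% | 98.2 / 88.3 |
| 40% | 1 | 4.17% | 22.54% | 18.5% | 95.8 / 86.2 |
| 20% | 0.5 | 6.24% | 14.60% | 42.7% | 93.8 / 84.4 |
| 40% | 0.5 | 13.71% | 30.32% | 45.2% | 86.3 / 77.7 |

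Asked at enrolment, Part One could be available for up to 100 of 100.

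**Does restriction to 1-month survivors weaken an alcohol association?**

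Assume 6-month death of 30% in heavy drinkers and 15% in others, a risk ratio of 2.0. Among survivors to 1 month the risk is (F6 − F1)/(1 − F1), where F1 and F6 are the proportions dead by months 1 and 6.
- Proportional hazards, k = 1: F1 = 1 − 0.70^(1/6) = 5.8% and 1 − 0.85^(1/6) = 2.7%. Survivor risks are 25.7% and 12.7%, ratio 2.03.
- Proportional hazards, k = 0.5: the exponent is (1/6)^0.5 = 0.408, so F1 = 13.6% and 6.4%. Survivor risks are 19.0% and 9.2%, ratio 2.08.
- Excess concentrated early, with F1 set at 12% and 3% (a fourfold ratio in month 1): 18/88 = 20.5% and 12/97 = 12.4%, ratio 1.65.

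The ratio falls only in the third case.

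**The case against.** The strongest reply is that no planned analysis is shown to suffer. Section 8.2.1 specifies no model relating alcohol to outcome. Section 4.3 gives behavioral health its own objective, "Describe the prevalence of behavioral health comorbidities after hospital discharge among people with HIV", and Section 5.1 uses that term for depression and alcohol, so placing alcohol under the separate comorbidity objective is an inference. The documented use of the screen is referral, which one form at 1 month serves; a patient who has already died cannot be referred. The pilot is also small. With an assumed 30 drinkers and 70 others at the death rates above, the standard error of the log risk ratio is √(1/9 − 1/30 + 1/10.5 − 1/70) = 0.40, so a ratio of 2.0 has a 95% interval of about 0.9 to 4.4. Section 8.2.1 already concedes low power for mortality and for multivariable work.

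This limits the point to exploratory and covariate-adjusted analyses. It does not remove the gap: Section 5.2.4 gives understanding outcome patterns as a reason for collecting these measures, and a score not taken before an early death cannot be recovered.

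A reader might go further and infer two things that the documents do not support. The first is that the alcohol association must be weakened if drinkers die early more often. The working shows that it is not under proportional hazards; it needs alcohol's relative effect to be concentrated in month 1, and nothing in the protocol says that it is. The second is that the prevalence of unhealthy drinking will be understated. The prevalence objective concerns the period after discharge, which a post-discharge screen suits, and no objective asks for pre-admission prevalence.

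**Conclusion.** The point stands as one of schedule and missing data. A pre-admission measure is collected only from patients who are alive and reached at about 1 month, while outcomes count from discharge. Under a constant hazard about 2-4 patients per 100 die before the screen, roughly 18% of 6-month deaths. With the assumed front-loaded shape the figures are about 6-14 per 100 and 43-45%. Patients not reached add to the number without a score.

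These figures rest on the protocol's one-year range, which describes hospitalized people with HIV generally rather than this trial's eligible group, on the two assumed curve shapes, and on a screen at exactly 1 month. The missing scores follow from the schedule alone; only their number is uncertain. Whether an association would be biased, and in which direction, cannot be settled from the documents.

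**What to change.** - Add the three Part One items to the enrolment list in Section 5.2.4, asked by research staff in pilot patients and historical controls alike.
- Keep Part Two at about 1 month.
- Pass the stored Part One score to the CHW, so that the referral rule in Appendix 12 is applied unchanged.
- State in Section 8.2.1 that pre-admission alcohol is analysed against outcomes from discharge in everyone enrolled (apart from deaths before discharge, which Section 8.1.1 already leaves out of the main analysis), and Part Two only against outcomes after the screen. Report how many patients have no 1-month screen and why.

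No new visit is needed: Section 6.3 already requires patients who are clinically stable and able to consent. The costs are a slightly longer enrolment interview, sensitive questions on wards where Section 9.4 acknowledges little privacy, and a score that must travel from research staff to the CHW. Collection in controls may be additional work, since the protocol does not say whether they are screened now.

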## 26. Appendix 13: Nyanja - Modified Alcohol Use Disorders Identification Test-Consumption

Kuyesa Kugwiritsa Ntchito Mowa Wosinthidwa (AUDIT-C) (Modified Alcohol Use Disorders Identification Test-Consumption (AUDIT-C))					
GAWO LOYAMBA: kumwa mowa musanalowe					
Mafunso	0 points	1 point	2 points	3 points	4 points
M'miyezi itatu musanalowe m'chipatala, pafupifupi, ni kangati pomwe mumamwa chili conse comwe kuli mowa?	Ayi	Mwezi uliwonse kapena kuchepera	2-4 pa mwezi	2-3 pa sabata	4+ pa sabata
Mwenze kumwa mabotolo angati ya mowa ngati muli pa tsiku lakumwa mowa?	0-2	3-4	5-6	7-9	10 kapena kuposa
Ndi nthawi ziti zimene mumwa zakumwa zofikira mabotolo yali 6 kapena zopitilila pa nthawi imodzi?	Ayi	Pasanathe mwezi uliwonse	Mwezi uliwonse	Mlungu uliwonse	Tsiku lililonse kapena pafupifupi tsiku lililonse
GAWO LACHIWIRI: kumwa mowa mutasiya					
Mafunso	0 points	1 point	2 points	3 points	4 points
Kuyambira kumasulidwa, ni kangati pomwe mumamwa chili conse comwe kuli mowa?	Ayi	Mwezi uliwonse kapena kuchepera	2-4 pa mwezi	2-3 pa sabata	4+ pa sabata
Nthawi yolozera upangiri wogwiritsa ntchito mowa mosayenera: 
 
• Zigoli za 3 kapena kupitilira apo a lowetsedwa kale ndi 2 kapena kupitilira apo atasiya
 
• Zigoli zitatu kapena kupitilira apo mutangotulutsidwa, posatengera kuti munalandira bwanji
 
					

Mawu a M'munsi:

#Ngati munthuyo anena kuti samamwa (mwachitsanzo, kudziletsa), siyani ziwiri zotsatirazi (zidumphani) Zakumwa zokhazikika zitha kuzindikirika motere:

- 1 lager (botolo la 12-ounce, Mosi / Castle, 3% mowa) = 1 unit
- 1 galasi la vinyo (5-ounce, 10% mowa) = 1 unit
- Chidebe chimodzi cha mowa wosawoneka bwino (1-lita, Chibuku Shake Shake, etc., 4% mowa) = mayunitsi 4
- Botolo limodzi la mizimu kuphatikizapo gin, vodka, 'junta', 'twojilijili' (botolo la 200 ml; 40% mowa) = mayunitsi 8
- 1 botolo la Cachasu (200 ml botolo; > 40% mowa) = mayunitsi 10

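### The drink-unit footnote counts a 5-ounce glass of 10% wine as 1 unit, but its own beer and spirits lines make it about 1.4 to 1.5, which lowers some wine drinkers' pre-admission AUDIT-C scores.

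*Combined protocol and SAP*

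**What the plan says.** Section 5.2.4 schedules an alcohol screen at one month. The form is the modified AUDIT-C in Appendix 12 (English), Appendix 13 (Nyanja) and Appendix 14 (Bemba). In the English form, two scored items of Part One (pre-admission drinking) carry the asterisk that points to the drink-unit footnote. One is the quantity item, "When you were drinking alcohol, on average, how many drinks did you have". The other asks "how often did you have 6 or more drinks* in one day".

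The footnote gives a volume, a strength and a unit count for five drinks:
- lager: "12-ounce bottle, Mosi/Castle, 3% alcohol) = 1 unit"
- wine: "5-ounce, 10% alcohol) = 1 unit"
- opaque beer: "1-liter, Chibuku Shake Shake, etc., 4% alcohol) = 4 units"
- spirits: "200 ml bottle; 40% alcohol) = 8 units"
- cachasu: "200 ml bottle; >40% alcohol) = 10 units"

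The Nyanja form repeats the wine line ("1 galasi la vinyo (5-ounce, 10% mowa) = 1 unit"), and so does the Bemba form.

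Part Two (post-discharge drinking) is one frequency question and uses no units. The form refers a patient for counseling by either of two paths: a pre-admission score of at least 3 with a post-discharge score of at least 2, or a post-discharge score of at least 3 alone. Section 5.3.2 uses an AUDIT-C cut of 3, together with having been referred, to choose up to 8 patients for extra interviews. Primary endpoint 7 in Section 4.4 concerns patients who seek services after screening and referral.

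**The concern.** A unit table should give the same count to the same amount of alcohol, whatever the drink. Four of the five lines can be checked from their own entries, and wine is the only one of them that departs clearly from the rest. Because the figure is multiplied by the number of glasses before scoring, the discrepancy grows with intake. Four glasses of wine (57 to 59 ml of alcohol) count as 4 drinks, while 1.5 litres of opaque beer (60 ml) count as 6.

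At stake is whether some wine drinkers fall below the pre-admission cut of 3. Through that cut it could affect who is referred, who counts as referred in primary endpoint 7, and who can be chosen for the extra interviews.

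**Working it through.** **Inputs.** Volumes, strengths and unit counts are from the Appendix 12 footnote. Item 2 points are from the same form: 0-2 drinks = 0, 3-4 = 1, 5-6 = 2, 7-9 = 3, 10 or more = 4. The documents do not say which ounce is meant, so I assume 29.57 ml (US) or 28.41 ml (imperial) and show both.

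**Alcohol per stated unit** = volume x strength / units.
- Opaque beer: 1000 x 0.04 / 4 = 10.0 ml.
- Spirits: 200 x 0.40 / 8 = 10.0 ml.
- Lager: 12 x 29.57 x 0.03 = 10.65 ml (imperial 10.23 ml).
- Wine: 5 x 29.57 x 0.10 = 14.79 ml (imperial 14.21 ml).
- Cachasu: the strength is given only as above 40%, so it cannot be tested exactly. It gives 10 ml per unit if the strength is 50% (200 x 0.50 / 10).

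The printed 1 unit for wine is therefore not reproduced. At 10 ml per unit, the glass is 14.79 / 10 = 1.48 units (imperial 1.42). Measured against the lager line it is 1.39. If wine were taken as the standard instead, opaque beer would be 40 / 14.79 = 2.7 units (imperial 2.8) against a stated 4, and spirits 80 / 14.79 = 5.4 (imperial 5.6) against a stated 8. No single unit fits all the lines.

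**Effect on item 2.** The form gives no rounding rule, so both rounding and truncation are shown.

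| Glasses | Points as printed | Units at 1.42-1.48 each | Points, rounded | Points, truncated |
|---|---|---|---|---|
| 1 | 0 | 1.42-1.48 | 0 | 0 |
| 2 | 0 | 2.84-2.96 | 1 | 0 |
| 3 | 1 | 4.26-4.44 | 1 | 1 |
| 4 | 1 | 5.68-5.91 | 2 | 2 |
| 5 | 2 | 7.10-7.39 | 3 | 3 |
| 6 | 2 | 8.52-8.87 | 3 | 3 |
| 7 | 3 | 9.94-10.35 | 4 | 3 or 4 |
| 8 | 3 | 11.4-11.8 | 4 | 4 |
| 9 | 3 | 12.8-13.3 | 4 | 4 |
| 10 | 4 | 14.2-14.8 | 4 | 4 |

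**Crossing the cut of 3 on Part One** (items 1 + 2 + 3).
- Four glasses, monthly or less: printed 1 + 1 + 0 = 2. On the consistent unit, 1 + 2 = 3 before item 3. The total is at least 3 under either rule.
- Two glasses, 2-4 times a month: printed 2 + 0 + 0 = 2. On the consistent unit, 2 + 1 + 0 = 3 if the total is rounded up, but still 2 if truncated.

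**Reaching the referral flag.** With a post-discharge score below 2, neither path is met whatever Part One says. With 3 or more, the second path refers regardless. So Part One decides only at exactly 2. One case that does not depend on rounding is a person who drinks 2-4 times a month before admission and after discharge, averages 1-2 glasses, and has occasional 5-glass days. As printed, item 1 = 2, item 2 = 0 and item 3 = 0 (5 units is under 6), for a total of 2 and no referral. On the consistent unit, 5 glasses are 7.1 to 7.4 units, so item 3 is at least 1 and the total at least 3. With a post-discharge score of 2, this person is referred.

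**The case against.** The best defence is that the documents never define a unit as 10 ml, that every line prints a whole number, and that 1.42 to 1.48 rounds to 1. It is true that the 10 ml is inferred. But lager is off that basis by 2 to 6% and wine by 42 to 48%. Rounding each glass also does not help, because the rounded figure is then multiplied by the number of glasses and scored.

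Other objections stand and limit the point:
- A reader might infer that every wine drinker is under-scored. That is not so: on item 2, 1, 3 and 10 or more glasses score the same either way, and 2 glasses change only if the total is rounded up.
- A reader might score the four-glass example as 4 on the consistent unit. That needs 5.7 to 5.9 drinks to be rounded to 6 for item 3, and the form has no such rule. The supported figure is at least 3.
- A reader might infer that a changed Part One score generally changes referral, and so primary endpoint 7. It does not. The four-glass drinker above has a post-discharge score of 1 if frequency stays the same, and is not referred in either case.
- A reader might infer a biased prevalence of unhealthy alcohol use. Exploratory objective 2 (Section 4.3) concerns comorbidities after discharge, and no section defines that prevalence from the Part One total.
- The documents do not show which entry on the wine line is wrong: the unit count, the glass size or the strength.

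**Conclusion.** The wine line is inconsistent with the other lines of its own table, and it is used in scoring. It counts a glass of 1.42 to 1.48 units as 1. It never raises a Part One score and lowers it at some intakes, with at least one crossing of the cut of 3 that holds under any rounding. Referral can change only at a post-discharge score of exactly 2. Through referral, so can selection for the extra interviews and the denominator of primary endpoint 7, if that denominator is read as the patients referred.

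This rests on the 10 ml per unit implied by two lines and nearly matched by a third, and on either ounce. The number of patients affected cannot be computed, because the documents give no share of wine drinkers. The effect is probably small. The 6-month outcome and the sample size are unaffected.

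**What to change.** Reconcile the wine line with the others in Appendices 12, 13 and 14. At the stated volume and strength it is about 1.5 units (1.48 with US ounces). If the glass size or the strength is the wrong entry, correct that instead: at 10% strength, 1 unit would be 10 / 0.10 = 100 ml.

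State the unit above the list (about 10 ml of alcohol) and give one rule for rounding the day's total before scoring. A flat 1.5 gives 3 x 1.5 = 4.5 at three glasses, a tie. Rounded up to 5, it would add an item 2 point and take a three-glass, monthly-or-less drinker from 1 + 1 = 2 to 1 + 2 = 3. Using 1.48 per glass avoids this (3 x 1.48 = 4.44, scored as 4). Leave the referral thresholds unchanged.

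The cost is one figure and a short note on three forms, with the ethics review that Section 9.2 requires for modifications. If screening data have already been collected, record which conversion was applied so that wine responses can be interpreted.
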